4.2 METHOD OF TREATMENT ASSIGNMENT AND BLINDING

This is a non-randomized, open-label study. After initial written informed consent has been obtained, all screening procedures and assessments have been completed, and eligibility has been established for a patient, the study site will obtain the patient's identification number and treatment assignment from an interactive voice or web-based response system (IxRS).

4.3 STUDY TREATMENT AND OTHER TREATMENTS RELEVANT TO THE STUDY DESIGN

The investigational medicinal products (IMP) for this study are atezolizumab and venetoclax. Carboplatin and etoposide are background treatments and are thus considered non-investigational medicinal products (NIMPs) in this study.

Rescue medications pre-medications, and supportive medications such as acetaminophen, ibuprofen, diphenhydramine, famotidine, cimetidine and other antihistamines, antipyretics, analgesics, corticosteroids, G-CSF, H₂-receptor antagonists, β_2 -adrenergic agonists are also considered NIMPs in this study.

4.3.1 Study Treatment Formulation, Packaging, and Handling

4.3.1.1 Atezolizumab

The atezolizumab Drug Product will be supplied by the Sponsor as a sterile liquid in a single-use, 20 mL glass vial. The vial contains approximately 20 mL (1200 mg) of atezolizumab solution.

For information on the formulation and handling of atezolizumab, refer to the Atezolizumab Pharmacy Manual and Investigator's Brochure.

4.3.1.2 Venetoclax

Patients will self-administer venetoclax tablets by mouth daily. Venetoclax is formulated as 100-mg tablets; patients may take up to eight 100-mg tablets daily to receive an 800-mg continual dose. Each dose of venetoclax will be taken with approximately 240 mL of water within 30 minutes after the patient's first meal of the day (e.g., breakfast). For continuous venetoclax dose (Days 1–21), patients should continue taking venetoclax without a break between cycles.

For information on the formulation and handling of venetoclax, refer to the Venetoclax Pharmacy Manual and Investigator's Brochure.

4.3.1.3 Carboplatin and Etoposide

Carboplatin and etoposide will be used in the commercially available formulation.

For information on the formulation, packaging, and handling of carboplatin and etoposide, refer to the prescribing information for each drug.

4.3.2 Study Treatment Dosage, Administration, Sequence, and Compliance

Atezolizumab will be given at fixed dose of 1200 mg by IV infusion every 21 [\pm 2] days in both induction and maintenance. For more information on the formulation, packaging, and handling of atezolizumab, please refer to the prescribing information.

Carboplatin and etoposide induction therapy will be administered as follows:

During induction, patients will be treated with carboplatin and etoposide chemotherapy. For information on the formulation, packaging, and handling of these therapies, please see the prescribing information for each drug.

Standard doses of each agent will be administered for a total of four 21-day cycles during induction.

 Carboplatin AUC 5 mg/mL min (Calvert formula dosing) IV infusion over 30–60 minutes on Day 1 of each cycle after completion of atezolizumab IV infusion with standard anti-emetics per local practice guidelines. Etoposide 100 mg/m² IV on Days 1–3 of each cycle. On Day 1 of each cycle, etoposide should be administered intravenously over 60 minutes following carboplatin administration. On Days 2 and 3 of each cycle, etoposide (100 mg/m²) should be administered intravenously over 60 minutes. Premedication should be administered according to local standard of care.

On Day 1 of each cycle, all eligible patients will receive treatment in the following order:
 Induction: atezolizumab → carboplatin → etoposide→ venetoclax
 Maintenance: atezolizumab → venetoclax

On Days 2 and 3, patients will receive etoposide infusions.

Because the effects of corticosteroids on T-cell proliferation have the potential to attenuate atezolizumab-mediated anti-tumor immune activity, premedication with corticosteroids should be minimized to the extent that is clinically feasible. Secondly, at the initiation of the induction phase of dose-escalation Arm B, cohorts will be treated without primary prophylactic G-CSF. The administration of secondary prophylactic G-CSF for high-frequency febrile neutropenia, severe neutropenia, or prolonged neutropenia must be discussed and agreed upon between the investigator and the Medical Monitor. Please refer to Appendix 10 or administration details, which are in accordance with institutional standards and ASCO, NCCN, or ESMO guidelines. Of note, if and once primary prophylactic G-CSF is deemed to be necessary as determined in the dose-escalation phase (see Section 3.1.2.2), then this requirement will be implemented during induction therapy for all subsequent patients.

For information on the formulation and handling of atezolizumab, see the pharmacy manual and the Atezolizumab Investigator's Brochure.

Administration of atezolizumab will be performed in a monitored setting where there is immediate access to trained personnel and adequate equipment and medicine to manage potentially serious reactions. For anaphylaxis precautions, see Appendix 8. Atezolizumab infusions will be administered per the instructions outlined in Table 2.

Cycles in which no chemotherapy is given do not count toward the total number of induction chemotherapy cycles.

After the induction phase, patients will begin maintenance therapy with atezolizumab plus venetoclax.

The suggested infusion times for carboplatin and etoposide may be adapted in accordance with local standard of care.

Any dose modification should be noted on the Study Drug Administration eCRF. Cases of accidental overdose or medication error, along with any associated adverse events, should be reported as described in Section 5.3.5.12.

Venetoclax—F. Hoffmann-La Roche Ltd Page 78 of 214 Protocol GO41864, Version 2 Administration of atezolizumab will be performed in a monitored setting where there is immediate access to trained personnel and adequate equipment and medicine to manage potentially serious reactions. For anaphylaxis precautions, see Appendix 8.

Guidelines for dose modification and treatment interruption or discontinuation for carboplatin and etoposide are provided in Sections 5.1.5 and 5.1.5.3.

4.3.2.1 Atezolizumab

All patients will receive 1200 mg atezolizumab administered by IV infusion on Day 1 of each 21-day cycle. The atezolizumab dose is fixed and is not dependent on body weight. Atezolizumab infusions will be administered per the instructions outlined in Table 2.

No dose modification for atezolizumab is allowed. Guidelines for treatment interruption or discontinuation are provided in Appendix 10 and Appendix 13. Guidance on study drug administration in the context of management of specific adverse events is provided in Section 5.

For further details on dose preparation, storage, and administration instructions for atezolizumab, please refer to the pharmacy manual and/or the Atezolizumab Investigator's Brochure.

4.3.2.2 Venetoclax

At the start of each cycle, patients will be supplied with sufficient venetoclax tablets for that cycle. A drug diary will be provided to the patient to record oral administration of doses, including the date and time of dosing. Patients will be instructed to return empty bottles or unused tablets.

The investigator is responsible for monitoring patient compliance by monitoring the patient diary and counting unused tablets. Patient compliance with the assigned daily dose of study medication will be assessed by standard pill counts. Previously distributed bottles will be returned to the clinic and tablets counted. Any discrepancy will be resolved with the patient at each clinic visit and documented in the patient record.

Each dose of venetoclax will be taken orally once daily with approximately 240 mL of water within approximately 30 minutes after the completion of breakfast or patient's first meal of the day. Patients should self-administer venetoclax at approximately the same time each morning. On days that PK sampling is required, the patient's first meal of the day and all study treatment doses should occur in the clinic to ensure accurate timing of the PK sampling. On those days, the time of each dose of venetoclax will be recorded to the nearest minute.

A meal containing approximately 30% of the total caloric content from fat is recommended to ensure adequate absorption of venetoclax. The following is an example of a breakfast that contains approximately 520 Kcal and has 30% of the total caloric content of the meal from fat that is, approximately 17 grams of fat: one box

Venetoclax—F. Hoffmann-La Roche Ltd Page 79 of 214 Protocol GO41864, Version 2 cereal (30–40 g), skim milk (240 mL), one boiled egg, one slice of toast (15 g) with 1 tablespoon of margarine (14 g). The toast and margarine may be replaced with one medium croissant or two large pancakes. If there is a substantial period of time between the patient's regular time of breakfast and their venetoclax dosing in the clinic on PK sampling days, the patients may have a low-fat snack in the morning. The patients must be instructed not to take their study treatment with the snack and to take their study treatments in the clinic after a meal.

Venetoclax tablets should be swallowed whole and never be chewed, cut, or crushed. If vomiting occurs within 15 minutes after taking venetoclax and all expelled tablets are still intact, another venetoclax dose should be taken, and the second dose should be noted in the drug diary. If tablets are not intact or if vomiting occurs more than 15 minutes after taking venetoclax, no replacement dose is to be taken. In cases where a dose of venetoclax is missed or forgotten, the patient should take the dose with food as soon as possible, ensuring that the dose is taken within 8 hours of the missed dose. Otherwise, the dose should not be taken.

Following the administration of atezolizumab and an observation period (see Table 2), patients will receive venetoclax.

Guidance on study drug administration in the context of management of specific adverse events is provided in Section 5.

	First Infusion	Subsequent Infusions
Atezolizumab infusion	 No premedication is allowed for the first infusion of atezolizumab. Record the patient's vital signs (pulse rate, respiratory rate, blood pressure, and temperature) within 60 minutes prior to starting the infusion of atezolizumab. Infuse atezolizumab over 60 (± 15) minutes. If clinically indicated, vital signs should be measured every 15 (± 5) minutes during the infusion and at 30 (± 10) minutes after the infusion. Patients should be informed about the possibility of delayed post-infusion symptoms and instructed to contact their study physician if they develop such symptoms. 	 If the patient experienced an IRR during any previous infusion of atezolizumab, premedication with an antihistamine and/or antipyretic may be administered for Cycle ≥ 2 and beyond at the discretion of the treating physician. Record the patient's vital signs (pulse rate, respiratory rate, blood pressure, and temperature) within 30 minutes before starting the infusion of atezolizumab. If the patient tolerated the first infusion of atezolizumab well without infusion-associated adverse events, the next infusion of atezolizumab may be infused over 30 (± 10) minutes. If no reaction occurs, continue subsequent infusions of atezolizumab over 30 (± 10) minutes. Continue to record vital signs within 30 minutes before starting the infusion of atezolizumab over 30 (± 10) minutes. Record vital signs during the infusion of atezolizumab.
Observation period after infusion of atezolizumab	 After the infusion of atezolizumab, the patient begins a 60minute observation period. Record the patient's vital signs (pulse rate, respiratory rate, blood pressure, and temperature) at 30 (±10) minutes after the infusion of atezolizumab. 	 If the patient tolerated the first or a subsequent infusion of atezolizumab (without premedication) well without infusion-associated adverse events, the observation period after the next and following infusions may be reduced to 30 minutes. If the patient experienced infusion-associated adverse events in the previous infusion, the observation period should be 60 minutes. If clinically indicated, record the patient's vital signs (pulse rate, respiratory rate, blood pressure, and temperature) at 15 (±10) minutes after the infusion of atezolizumab.

 Table 2
 Administration of First and Subsequent Atezolizumab Infusions

IRR=infusion-related reaction.

Guidelines for medical management of infusion-related reactions (IRRs) are provided in Appendix 13.

4.3.2.3 Atezolizumab/Venetoclax

The following rules apply as long as neither atezolizumab nor venetoclax has been permanently discontinued:

- Treatment cycles will normally begin with dosing of atezolizumab on Day 1 of each 21-day cycle. If atezolizumab is delayed for related toxicity, it is recommended that the venetoclax is also delayed. However, if venetoclax is delayed for related toxicity, atezolizumab may be continued, if considered appropriate at the discretion of the investigator.
- In case of delays in dosing of one study drug (atezolizumab or venetoclax) for drug-related toxicity while the other study drug (atezolizumab or venetoclax) is given as planned, it is recommended that the study drug being delayed be administered at the next scheduled infusion (i.e., at the next scheduled 21-day cycle).

Carboplatin and/or etoposide may be administered as planned in the event that atezolizumab and/or venetoclax dose(s) are delayed. If carboplatin and/or etoposide doses must be delayed, atezolizumab and/or venetoclax may be administered as planned.

Guidelines for treatment interruption or discontinuation are provided in Sections 4.6.1 and 5.1.5.

4.3.2.4 Carboplatin and Etoposide Carboplatin

During the induction phase, carboplatin will be administered after completion of atezolizumab by IV infusion over 30–60 minutes to achieve an initial target AUC of 5 mg/mL/min (Calvert formula dosing) with standard anti-emetics per local practice guidelines. Because the effects of corticosteroids on T-cell proliferation have the potential to attenuate atezolizumab-mediated anti-tumor immune activity, premedication with corticosteroids should be minimized to the extent that is clinically feasible (see Section 4.4.2). Carboplatin infusion times may be adapted in accordance with local standard of care.

The carboplatin dose of AUC 5 will be calculated using the Calvert formula (Calvert et al. 1989):

Calvert Formula

Total dose (mg)=(target AUC)×(glomerular filtration rate [GFR]+25)

NOTE: The GFR used in the Calvert formula to calculate AUC-based dosing should not exceed 125 mL/min.

For the purposes of this protocol, the GFR is considered to be equivalent to the CRCL. The CRCL is calculated by institutional guidelines or by the method of Cockcroft and Gault (1976) using the following formula:

$$CRCL = \frac{(140 - age) \times (wt)}{72 \times Scr} (\times 0.85 \text{ if female})$$

Where: CRCL=creatinine clearance in mL/min age=patient's age in years wt=patient's weight in kg Scr=serum creatinine in mg/dL

NOTE: For patients with an abnormally low serum creatinine level, estimate the GFR through use of a minimum creatinine level of 0.8 mg/dL or cap the estimated GFR at 125 mL/min.

If a patient's GFR is estimated based on serum creatinine measurements by the isotope dilution mass spectroscopy method, the U.S. Food and Drug Administration (FDA) recommends that physicians consider capping the dose of carboplatin for desired exposure (AUC) to avoid potential toxicity due to overdosing. On the basis of the Calvert formula described in the carboplatin label, the maximum doses can be calculated as follows:

Maximum carboplatin dose (mg)=target AUC (mg×min/mL)×(GFR+25 mL/min)

The maximum dose is based on a GFR estimate that is capped at 125 mL/min for patients with normal renal function. No higher estimated GFR values should be used.

For a target AUC = 5, the maximum dose is $5 \times (125+25) = 5 \times 150 = 750$ mg. For a target AUC = 4, the maximum dose is $4 \times (125+25) = 4 \times 150 = 600$ mg.

Refer to the FDA's communication regarding carboplatin dosing with use of the following Web site for more details:

http://www.fda.gov/aboutfda/centersoffices/officeofmedicalproductsandtobacco/cder/ucm228974.htm

Guidelines for treatment interruption or discontinuation are provided in Sections 4.6.1 and 5.1.5.

Etoposide

During the induction phase, on Day 1 of each cycle, etoposide (100 mg/m²) will be administered by IV infusion over 60 minutes following carboplatin administration. On Days 2 and 3 of each cycle, etoposide (100 mg/m²) will be administered by IV infusion over 60 minutes. Premedication should be administered according to local standard of care. Because the effects of corticosteroids on T-cell proliferation have the potential to attenuate atezolizumab-mediated anti-tumor immune activity, premedication with

corticosteroids should be minimized to the extent that is clinically feasible (see Section 4.4.2). Etoposide infusion times may be adapted in accordance with local standard of care.

Guidelines for treatment interruption or discontinuation are provided in Sections 4.6.1 and 5.1.5.

Refer to the local prescribing information for material on potential drug interactions between etoposide or carboplatin and concomitant medications.

4.3.3 Investigational Medicinal Product Accountability

All IMPs required for completion of this study will be provided by the Sponsor. The study site will acknowledge receipt of IMPs supplied by the Sponsor using the IxRS to confirm the shipment condition and content. Any damaged shipments will be replaced.

IMPs will either be disposed of at the study site according to the study site's institutional standard operating procedure or be returned to the Sponsor with the appropriate documentation. The site's method of destroying Sponsor-supplied IMPs must be agreed to by the Sponsor. The site must obtain written authorization from the Sponsor before any Sponsor-supplied IMP is destroyed, and IMP destruction must be documented on the appropriate form.

Accurate records of all IMPs received at, dispensed from, returned to, and disposed of by the study site should be recorded on the Drug Inventory Log.

4.3.4 Continued Access to Atezolizumab and Venetoclax

The Sponsor will offer continued access to Roche IMPs venetoclax and atezolizumab free of charge to eligible patients in accordance with the Roche Global Policy on Continued Access to Investigational Medicinal Product, as outlined below.

A patient will be eligible to receive Roche IMPs venetoclax and atezolizumab after completing the study if all of the following conditions are met:

- The patient has a life-threatening or severe medical condition and requires continued Roche IMP treatment for his or her well-being
- There are no appropriate alternative treatments available to the patient
- The patient and his or her doctor comply with and satisfy any legal or regulatory requirements that apply to them

A patient will not be eligible to receive Roche IMPs venetoclax and atezolizumab after completing the study if any of the following conditions are met:

• The Roche IMP is commercially marketed in the patient's country and is reasonably accessible to the patient (e.g., is covered by the patient's insurance or wouldn't otherwise create a financial hardship for the patient)

Venetoclax—F. Hoffmann-La Roche Ltd Page 84 of 214 Protocol GO41864, Version 2

- The Sponsor has discontinued development of the IMP or data suggest that the IMP is not effective for breast cancer
- The Sponsor has reasonable safety concerns regarding the IMP as treatment for breast cancer
- Provision of the Roche IMP is not permitted under the laws and regulations of the patient's country

The Roche Global Policy on Continued Access to Investigational Medicinal Product is available at the following website:

http://www.roche.com/policy_continued_access_to_investigational_medicines.pdf

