Immune-related adverse events are consistent with the role of the PD-L1/PD-1 pathway in regulating peripheral tolerance. Given the mechanism of action of atezolizumab, events associated with inflammation and/or immune-related adverse events are expected. Immune-related adverse events associated with atezolizumab include pneumonitis, hepatitis, colitis, pancreatitis, diabetes mellitus, hypothyroidism, hyperthyroidism, adrenal insufficiency, hypophysitis, Guillain-Barré syndrome, myasthenic syndrome/myasthenia gravis, meningoencephalitis, myocarditis, and nephritis.

Atezolizumab is approved for the treatment of urothelial carcinoma, NSCLC, SCLC, and triple-negative breast cancer.

Refer to the Atezolizumab Investigator's Brochure for details on nonclinical and clinical studies.

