In the EU, venetoclax in combination with rituximab is indicated for the treatment of adult patients with CLL who have received at least 1 prior therapy. Monotherapy is indicated for the treatment of CLL in the presence of 17p deletion or *TP53* mutation in adult patients who are unsuitable for or have failed a B-cell receptor pathway inhibitor, or in the absence of 17p deletion or *TP53* mutation in adult patients who have failed both chemoimmunotherapy and a B-cell receptor pathway inhibitor.

Moreover, data with venetoclax in solid tumors such as ER-positive, Bcl-2 positive metastatic breast cancer (Lok et al. 2019) show promising activity. In a Phase Ib dose-escalation study, venetoclax dosed at 200, 400, 600, or 800 mg/daily in combination with tamoxifen 20 mg/daily, was shown to be well tolerated with no dose-limiting toxicities (DLTs) being observed in any of the cohorts and the maximum tolerated dose (MTD) not being reached. Efficacy was promising, with an observed ORR of 54% and clinical benefit rate (CBR) of 75% for the 800-mg cohort, comparing favorably with historical studies of patients treated with tamoxifen in first-line relapse (e.g., ORR 17%–33% and CBR 38%–56%).

Refer to the Venetoclax Investigator's Brochure for details on nonclinical and clinical studies.

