4.1.1 Inclusion Criteria

Dose Escalation, Maintenance Arm A

- Patients with ES-SCLC who have completed 4-6 cycles of carboplatin and etoposide induction chemotherapy, with or without *atezolizumab*, as their first-line therapy for extensive-stage disease and have responded (CR or PR) or have SD are eligible for the maintenance arm of the study.
- All side effects attributed to prior anti-cancer therapy must have resolved to Grade 1 or baseline.
- A maximum of 8 weeks (56 days) is allowed between last chemotherapy dose (Cycle 4, Day 3) given in induction and the start of maintenance therapy.

Dose Escalation, Induction Arm B

- Patients with no prior systemic treatment for ES-SCLC are eligible for this study.
- ANC \geq 1,500 cells/µL without granulocyte colony-stimulating factor support

Dose Expansion, Maintenance-Only

• Patients with ES-SCLC who have completed 4 cycles of carboplatin and etoposide induction chemotherapy and at least 3 cycles of *atezolizumab* as their first-line therapy for extensive-stage disease and have *responded* (*CR or PR*) or have SD are eligible for the maintenance arm of the study.

Dose Escalation (Arms A and B) and Dose Expansion

- Signed Informed Consent Form
- Age \geq 18 years at time of signing Informed Consent Form
- Ability to comply with the study protocol, in the investigator's judgment
- ECOG performance status of 0 or 1
- Patients must be able to swallow pills
- Histologically or cytologically confirmed diagnosis of ES-SCLC per the Veterans Administration Lung Study Group (VALG) staging system
- Patients who received prior chemoradiotherapy for limited-stage SCLC must have been treated with curative intent and experienced a treatment-free interval of at least 6 months since last chemotherapy, radiotherapy, or chemoradiotherapy cycle prior to diagnosis of ES-SCLC
- Patients with a history of treated CNS metastases that are currently asymptomatic are eligible, provided they meet all of the following criteria:
 - Only supratentorial and cerebellar metastases allowed (i.e., no metastases to midbrain, pons, medulla or spinal cord)
 - No ongoing requirement for corticosteroids as therapy for CNS disease
 - No evidence of interim progression between the completion of CNS-directed therapy and enrollment
 - Patients with new asymptomatic CNS metastases detected at the screening scan must receive radiation therapy and/or surgery for CNS metastases.

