Women of childbearing potential must have a negative serum pregnancy test result within 14 days prior to initiation of study drug.

- Spinal cord compression not definitively treated with surgery and/or radiation or previously diagnosed and treated spinal cord compression without evidence that disease has been clinically stable for ≥1 week prior to enrollment
- Leptomeningeal disease
- Uncontrolled pleural effusion, pericardial effusion, or ascites requiring recurrent drainage procedures (once a month or more frequently)

Patients with indwelling catheters (e.g., PleurX[®]) are allowed regardless of drainage frequency.

- Uncontrolled or symptomatic hypercalcemia (ionized calcium > 1.5 mmol/L, total serum calcium > 12 mg/dL, or corrected calcium > ULN)
- History of malignancy other than SCLC within 5 years prior to enrollment, with the exception of those with a negligible risk of metastasis or death (e.g., expected 5-year OS > 90%) treated with expected curative outcome (such as adequately treated carcinoma in situ of the cervix, basal or squamous cell cancer of the skin, localized prostate cancer treated surgically with curative intent, ductal carcinoma in situ treated surgically with curative intent)
- History of autoimmune disease, including but not limited to myasthenia gravis, myositis, autoimmune hepatitis, systemic lupus erythematosus, rheumatoid arthritis, inflammatory bowel disease, vascular thrombosis associated with antiphospholipid syndrome, Wegener's granulomatosis, Sjögren's syndrome, Guillain-Barré syndrome, multiple sclerosis, vasculitis, or glomerulonephritis

Patients with a history of autoimmune-mediated hypothyroidism on a stable dose of thyroid replacement hormone are eligible for this study.

Patients with controlled Type I diabetes mellitus on a stable dose of insulin regimen are eligible for this study.

Patients with eczema, psoriasis, lichen simplex chronicus, or vitiligo with dermatologic manifestations only (e.g., no psoriatic arthritis) are permitted provided that they meet the following conditions:

- Rash must cover less than 10% of body surface area.

- Disease is well-controlled at baseline and only requiring low potency topical steroids.
- No acute exacerbations of underlying condition within the last 12 months requiring treatment with either psoralen plus ultraviolet A radiation (PUVA), methotrexate, retinoids, biologic agents, oral calcineurin inhibitors, or high potency or oral topical steroids

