5.3.5.10 Lack of Efficacy or Worsening of SCLC

Events that are clearly consistent with the expected pattern of progression of the underlying disease should not be recorded as adverse events. These data will be captured as efficacy assessment data only. In most cases, the expected pattern of progression will be based on RECIST v1.1. In rare cases, the determination of clinical progression will be based on symptomatic deterioration. However, every effort should be made to document progression through use of objective criteria. If there is any uncertainty as to whether an event is due to disease progression, it should be reported as an adverse event.

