5.3.5.11 Hospitalization or Prolonged Hospitalization

Any adverse event that results in hospitalization (i.e., inpatient admission to a hospital) or prolonged hospitalization should be documented and reported as a serious adverse event (per the definition of serious adverse event in Section 5.2.2), except as outlined below.

An event that leads to hospitalization under the following circumstances should not be reported as an adverse event or a serious adverse event:

- Hospitalization for respite care
- Planned hospitalization required by the protocol (e.g., for study treatment administration or performance of an efficacy measurement for the study)

• Hospitalization for a preexisting condition, provided that all of the following criteria are met:

The hospitalization was planned prior to the study or was scheduled during the study when elective surgery became necessary because of the expected normal progression of the disease

The patient has not experienced an adverse event

• Hospitalization due solely to progression of the underlying SCLC

An event that leads to hospitalization under the following circumstances is not considered to be a serious adverse event, but should be reported as an adverse event instead:

Hospitalization that was necessary because of patient requirement for outpatient care outside of normal outpatient clinic operating hours

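### The post-study access rule in Section 4.3.4 tests efficacy and safety against breast cancer, but the trial enrols only ES-SCLC

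*Combined protocol and SAP*

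**What the plan says.** Section 4.3.4 offers continued access to both investigational products, in line with a sponsor-wide policy that it outlines and links to. A patient must meet all of three positive conditions. In summary, these are a severe or life-threatening condition with a need for continued treatment, no suitable alternative, and compliance with legal requirements. Any one of four exclusion bullets then ends eligibility.

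The second exclusion bullet applies if development of the product has stopped, or if "data suggest that the IMP is not effective for breast cancer". The third reads: "The Sponsor has reasonable safety concerns regarding the IMP as treatment for breast cancer". The first and fourth concern commercial availability and local law, and neither names a disease.

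The population is defined in Section 4.1.1, in the criteria common to dose escalation (Arms A and B) and dose expansion: "Histologically or cytologically confirmed diagnosis of ES-SCLC per the Veterans Administration Lung Study Group (VALG) staging system". Section 4.1.2 excludes "History of malignancy other than SCLC within 5 years prior to enrollment", apart from cancers with negligible risk of metastasis or death that were treated with an expected cure.

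**The concern.** Two operative bullets judge the drugs by their performance in a disease that the trial does not study. Taken literally, this can go wrong in two directions:

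- Evidence of inefficacy or harm in SCLC, which this trial is meant to help generate, would not trigger either ground.
- Evidence of inefficacy or harm in breast cancer could trigger them for a patient with lung cancer.

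This is the protocol's only written rule on who may be supplied after the study. Patients could still be on treatment when it is needed. Treatment may continue for as long as there is clinical benefit, the end of study is expected 24 months after the last enrolment, and the sponsor may stop the study at any time (Section 3.2).

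**Working it through.** The plan gives no figure to reproduce. The check compares the exclusion list with the rest of the document.

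**1. Count the grounds in Section 4.3.4.** The second bullet joins two alternatives, so the four bullets hold five separate grounds.

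| Bullet | Ground | Disease named |
|---|---|---|
| 1 | Marketed and reasonably accessible | none |
| 2, first half | Development discontinued | none |
| 2, second half | Data suggest lack of efficacy | breast cancer |
| 3 | Reasonable safety concerns | breast cancer |
| 4 | Supply not permitted by law | none |

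Grounds naming breast cancer: 2 of 5. Grounds naming SCLC: 0 of 5. Grounds naming no disease: 5 − 2 = 3. Safety grounds naming breast cancer: 1 of 1. Halves of the efficacy and development bullet naming it: 1 of 2.

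**2. Compare with the population.** Section 4.1.1 requires confirmed ES-SCLC in every cohort. Section 4.1.2 removes patients with another recent malignancy, apart from negligible-risk cases. Breast cancer is not a study indication for any enrolled patient.

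**3. Compare with other operative rules.** Where the adverse event rules need a disease, they name the right one. Section 5.3.5.10 is headed "Lack of Efficacy or Worsening of SCLC", and Section 5.3.5.11 exempts "Hospitalization due solely to progression of the underlying SCLC".

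**4. Look for a passage that explains or corrects the wording.** Breast cancer appears elsewhere only as supporting material:

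- Section 1.4: "Atezolizumab is approved for the treatment of urothelial carcinoma, NSCLC, SCLC, and triple-negative breast cancer".
- Section 1.5, on "data with venetoclax in solid tumors such as ER-positive, Bcl-2 positive metastatic breast cancer".
- Section 3.3.2.1, where breast cancer studies support the 800 mg venetoclax dose.
- A title in the reference list, and general RECIST wording on breast disease in Appendix 5.

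None of these makes breast cancer relevant to post-study supply for these patients.

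**5. Work through the literal consequences.** The false-denial direction is theoretical at present. Sections 1.5 and 3.3.2.1 describe the venetoclax breast cancer results favourably, and Section 1.4 lists a breast cancer approval for atezolizumab. The false-permission direction is the practical gap: inefficacy or harm specific to SCLC is not a listed ground unless development has also been discontinued.

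The wording looks like text carried over from a breast cancer protocol. A footnote to Table 2 of Appendix 4, about next-line therapy that is purely antihormonal, also fits SCLC poorly. The origin is inference, and the finding does not depend on it.

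**The case against.** The strongest reply concerns weight, because the wording itself is not in dispute.

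- **The intended disease is obvious.** Anyone reading the section inside an ES-SCLC protocol would see it, and the bullets only outline a sponsor policy. This is fair as a forecast of how the rule would be read. The policy text is not in the documents, however, so it cannot be shown to cure the wording, and sites and ethics committees receive the bullets as written.
- **The positive conditions cover much of the same ground.** A patient must need continued treatment for his or her well-being, which is hard to argue for a drug shown to be ineffective or unsafe in that patient's disease. This stands and narrows the gap. It is still a judgement about the individual patient and does not supply an SCLC safety ground.
- **The marketed-product bullet limits reach.** Section 1.2 describes atezolizumab with carboplatin and etoposide as approved for first-line ES-SCLC in the United States and European Union. Section 1.5 describes venetoclax as approved in both regions for other diseases. This also narrows the issue, but the documents do not say whether venetoclax would be reasonably accessible for SCLC.
- **On-study protection is intact.** Sections 4.6.1 and 4.6.3 allow treatment or the whole study to be stopped on safety grounds. This is true, but those rules do not govern supply after the study.
- **The counts describe wording and do not measure harm.** This is accepted. The counts locate the error and are not an effect size.

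**Conclusion.** The concern holds. Section 4.3.4 names the wrong disease in 2 of its 5 exclusion grounds: its only safety ground, and the data-based half of the efficacy and development bullet. The ground for discontinued development, the other two bullets and the three positive conditions are unaffected.

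The error is minor. It shows no demonstrated harm or wrongful denial, and it has no bearing on any endpoint, dose-limiting toxicity rule, sample size or analysis. The number of patients who might be affected cannot be derived from the documents, and none is claimed. The conclusion rests on reading the bullets as written. How the sponsor would apply them depends on a policy that is linked but not reproduced.

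**What to change.** Replace breast cancer with SCLC in the second and third exclusion bullets of Section 4.3.4. The cost is one term changed in two bullets of one section, which can go into the next amendment. Trial conduct and analysis do not change.
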